### 3.5. Interim Analysis (IA)

One IA is planned for this study and will be conducted at the time of dose selection for POC. The POC dose will be selected based on cumulative available safety, tolerability, PK and PD data based on the MAD data. Since there is no IA during the POC part of the study, there is no impact on the type 1 error.

### 3.6. Timing of Analyses

The following analyses are planned:

- An IA will be performed during the last cohort of the MAD portion to determine dose selection for the POC portion.
- The final analysis will be performed when all patients have either completed the POC safety follow up or withdrawn from the study.
- Safety analyses will be performed for DMC reviews throughout the study to evaluate accumulating safety data and make dose escalation decisions. The frequency and details of the content and format of the safety review meetings are described in the DMC charter and SAP and applicable mock shells.

## 4. DATA ANALYSIS CONSIDERATIONS

All analyses will be conducted based on SAS 9.3 or higher.

All data in the database will be presented in by-patient data listings.

Unless otherwise stated, all listings will be sorted by study phase, treatment group, patient number, and assessment date (and time, if available). If assessment date is missing, chronological visit will be used for sorting.

Unless stated otherwise, continuous data will be summarized by treatment group based on number of patients (n), mean, median, standard deviation (SD), 25th percentile/first quartile (Q1), 75th percentile/third quartile (Q3), minimum value, and maximum value.

The geometric % coefficient of variation (CV) is calculated as  $100 * \sqrt{\exp(SD\log^2) - 1}$  where SDlog is the SD of log-transformed values.

Unless stated otherwise, categorical data will be summarized by treatment group using n and percentage based on the number of non-missing values.

- The number of missing values will be presented as a separate category with no percentage, but only if one or more patients are missing data.
- Counts of zero will be presented without percentages.

Sponsor: Boston Pharmaceuticals, Inc.  
Protocol Number: BOS161721-02  
SAP Version and Date: Version 4.0, 23Apr2021

Statistics will be presented in the summary tables based on the following:

- Minimum and maximum: same number of significant digits as the raw value
- Mean, median, Q1, and Q3: one additional decimal place to that reported for minimum and maximum
- SD: two additional decimal places than presented for the minimum and maximum
- Percentages: reported to one decimal place with the exception of 100% which will be displayed without decimals.
- P-values will be reported to four decimal places. If the value is below 0.0001 it will be noted as < 0.0001; if the value above 0.9999 it will be noted as > 0.9999.

Unless otherwise noted, statistical inference will be based on a 10% significance level (i.e. 90% confidence intervals will be produced).

Statistical testing will be performed on data from the Phase 2 study.

Numbering for data displays will be based on ICH E3.

#### 4.1. Stratification and Covariates

[figure not shown]
The effects of noncompliance, background therapy use, treatment discontinuations, premature withdrawal from study and covariates will be assessed to determine the impact on the general applicability of results from this study. Exploratory analyses of the data may be conducted as deemed appropriate to evaluate factors for which analyses are not controlled.

Continuous efficacy endpoints will be assessed via analysis of variance (ANOVA) or analysis of covariance (ANCOVA) when applicable, adjusting for the baseline value.

Sensitivity analyses of the primary efficacy endpoint may be performed with covariates defined based on the subgroups in section 4.2.

#### 4.2. Evaluation of Subgroups

CCI

Sponsor: Boston Pharmaceuticals, Inc.  
Protocol Number: BOS161721-02  
SAP Version and Date: Version 4.0, 23Apr2021

The patient will be excluded from subgroup analyses if they are missing the subgroup parameter at baseline. In case of missing data, LOCF methods consistent with the primary efficacy analysis described in Section 7.1 will be used for determination of baseline CLASI and SLEDAI.

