## 5.4. Baseline, Post-Baseline Changes, and LOCF

Unless stated otherwise, baseline and post-baseline change values will be based on the following:

- Baseline will be based on the last non-missing value collected prior to or on the date/time of first dose of study drug.
- Post-baseline values will be those collected after the date/time of first dose of study drug.
- Change from baseline is defined as: value – baseline value.
- Percentage change from baseline is defined as:  $[(\text{value} - \text{baseline value}) / \text{baseline value}] * 100$ . Patients with baseline values of zero are excluded due to division by zero.
- Most extreme change: The maximum most extreme change will be the maximum post-baseline change value; the minimum most extreme change will be the smallest post-baseline change value. This calculation will consider all assessments collected after the first dose of study drug, scheduled or unscheduled.
- LOCF:
  - Imputation rules for assessments that include multiple components:
    - In case of missing laboratory components, lab values from the most recent unscheduled visit  $\leq 14$  days after the nominal visit will be utilized. If lab values are not available from an unscheduled visit  $\leq 14$  days after the visit, laboratory data will be carried forward from the most recent laboratory assessment  $\leq 30$  (scheduled or unscheduled) days prior to the nominal visit.
    - In case of missing non-laboratory components, no imputation will be performed.
  - In case of missing the entire score for an assessment, imputation will be based on LOCF. LOCF will only be implemented with the most recent prior visit (including unscheduled assessments). If the most recent prior visit is missing, occurred more than 30 days before (current visit date – most recent prior visit date  $> 30$ ), or is not evaluable, LOCF is not implemented. See Section 7 for further details. Additional details regarding LOCF for components for specific assessments are described in Section 7.
  - Observed values do not incorporate any imputations and are presented as collected.

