#### 6.4. Demographic and Baseline Characteristics

Patient demographics and baseline characteristics will be summarized in the SS. These will include age (years), sex (Male / Female), ethnicity (Hispanic or Latino / Not Hispanic or Latino), race (American Indian or Alaska Native / Asian / Black or African American / Native Hawaiian or Pacific Islander / White / Other), geographic regions (North America / South or Central America / Eastern Europe), baseline height (cm), baseline weight (kg), and baseline BMI ( $\text{kg}/\text{m}^2$ ). Age is reported as collected in the clinical database and will also be categorized as a categorical variable ( $\leq 45$ ,  $> 45$ - $< 65$ ,  $\geq 65$ ) for reporting. Patient eligibility for central review will be summarized. Childbearing potential and birth control methods for female and male patients will be summarized for the DMC meetings and interim analysis only. Demographics and baseline characteristics will be summarized overall, by study phase, and treatment group.

Baseline disease characteristics will also be summarized in the FAS. The SLEDAI total score, PGA, CLASI total activity score, CLASI total damage score, ACR-28 sum of swelling, ACR-28 sum of tenderness, ACR-28 sum of active joints (swelling and tenderness in the same joint) and SLICC/ACR damage index total score will be summarized at baseline. Frequencies and percentages of patients with SLEDAI presence by component, ACR-28 loss of functional range interfering with life and ACR-28 impairment of basic activities from inflammation as well as BILAG grades by body organ system will be presented. Frequency and percentage of patients with each organ system disease on BILAG SLE history will be summarized. Frequency and percentage of patients with SLICC criteria for SLE will be summarized. Frequencies and percentages of patients with CLASI Activity Score ( $< 8$  vs.  $\geq 8$ ), SLEDAI-2K ( $< 10$  vs.  $\geq 10$ ) and baseline corticosteroid use (0,  $< 7.5$ ,  $\geq 7.5$ ,  $< 10$ ,  $\geq 10$  mg/day), will be presented. In case of missing data, LOCF methods consistent with the primary efficacy analysis described in Section 7.1 will be used for baseline disease characteristics summaries.

Frequencies and percentages of patients will also be presented for the following characteristics:

- Positive anti-ds-DNA
- Low C3 and/or C4

Sponsor: Boston Pharmaceuticals, Inc.  
Protocol Number: BOS161721-02  
SAP Version and Date: Version 4.0, 23Apr2021

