#### **Missing Data:**

- **Pre-Treatment:** If a patient is missing data during the pre-treatment period for SLEDAI-2K, PGA, or BILAG, the patient will be excluded from the primary efficacy analysis.

- **Overall SRI-4 Components:** Missing data at Day 210 for overall components for SLEDAI-2K, BILAG, and PGA will be addressed by employing a LOCF analysis within each overall component as described in Section 5.4. For example, if a patient has data for SLEDAI-2K and BILAG at Day 210 but is missing PGA at Day 210, the PGA component would employ LOCF as described in Section 5.4. If the overall component is missing from Day 180 through Day 210 and the patient is not a medication failure on or prior to Day 210 and did not withdraw/discontinue treatment prior to Day 180, the SRI-4 response at Day 210 will be considered not evaluable.
- **Individual Items Contributing to Overall SRI-4 Components:** Data collection and scoring will be performed in the clinical database for BILAG, SLEDAI-2K, and PGA. If missing individual items contributing to any of the overall components occurs for Day 210, the overall component will be recalculated per the Table 1.

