| SLEDAI-2K | 
If lab values are missing at Day 210, lab values will be imputed based on the below hierarchy of determination:
 
(1) If any unscheduled laboratory assessments occurred <=14 days after the Day 210 visit, the laboratory values at the most recent unscheduled laboratory assessment will be used for the determination of missing laboratory SLEDAI-2K criteria. For example, if platelet count is missing at Day 210 and an unscheduled laboratory assessment occurs 10 days after the Day 210 visit date, the platelet count from the unscheduled laboratory assessment would be used to determine if the patient had thrombocytopenia at Day 210 for SLEDAI-2K.
 
(2) Else if #1 does not occur or lab values are not available at the unscheduled visit noted in #1, the laboratory data will be carried forward from the most recent laboratory assessment (scheduled or unscheduled) <=30 days prior to the Day 210 nominal visit to make the SLEDAI-2K determination. For example, if a patient is missing thrombocytopenia and leukopenia SLEDAI-2K components at Day 210, they have an unscheduled lab assessment 10 days earlier with platelet counts populated and WBC not populated, and they have a Day 180 assessment within 30 days of the Day 210 visit with both platelets and WBC present, the platelet value from the unscheduled visit would be carried forward to the Day 210 for thrombocytopenia component designation and the WBC value would be carried forward from the Day 180 assessment to Day 210 for the Leukopenia component designation.
 
(3) If the lab components for SLEDAI-2K are missing from Day 210 and no unscheduled laboratory assessments occur within 14 days after or 30 days prior to the Day 210 assessment, the lab components from Day 180 will be carried forward, if available and if Day 180 occurred within 30 days of Day 210.
 
Otherwise, no non-lab individual SLEDAI-2K components will be carried forward. If non-lab individual components are missing at Day 210, the entire SLEDAI-2K score from Day 180 will be carried forward. If Day 180 is missing, occurred more than 30 days before Day 210, or is not
 |

|     |   |
|-----|---|

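### The rule for filling missing baseline SLEDAI-2K lab items looks forward 14 days before it looks back, with no exception for Day 0, and so conflicts with the plan's pre-dose definition of baseline

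*SAP*

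**What the plan says.** All references are to SAP version 4.0.

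- **Section 4.2 (subgroups):** where data are missing, "LOCF methods consistent with the primary efficacy analysis described in Section 7.1 will be used for determination of baseline CLASI and SLEDAI".
- **Section 6.4 (baseline characteristics):** "LOCF methods consistent with the primary efficacy analysis described in Section 7.1 will be used for baseline disease characteristics summaries". This section tabulates SLEDAI-2K as below 10 or at least 10, and crosses that split with anti-dsDNA and complement status.
- **Section 5.4, LOCF rules, any nominal visit:** "In case of missing laboratory components, lab values from the most recent unscheduled visit" within 14 "days after the nominal visit will be utilized. If lab values are not available from an unscheduled visit" in that window, the rule turns to the most recent lab from the 30 days before the visit.
- **Section 7.1.1, Table 1, SLEDAI-2K row (written for Day 210):** the order is the same. If an unscheduled lab falls within 14 days after the visit, "the laboratory values at the most recent unscheduled laboratory assessment will be used for the determination of missing laboratory SLEDAI-2K criteria". The look-back step opens with "Else if #1 does not occur or lab values are not available at the unscheduled visit noted in #1".
- **Section 5.4, baseline:** "Baseline will be based on the last non-missing value collected prior to or on the date/time of first dose of study drug". Later values are classed as post-baseline. The list holding this definition gives way wherever another section states something different.
- **Section 7.1.1, missing data:** "If a patient is missing data during the pre-treatment period for SLEDAI-2K, PGA, or BILAG, the patient will be excluded from the primary efficacy analysis".

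The revision log lists the baseline LOCF text as a version 4.0 clarification covering both the summaries and the subgroups, so it was added deliberately.

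**The concern.** Looking forward is tolerable at Day 210, where a lab drawn a few days late still describes the patient near the end of treatment. At Day 0 the same step crosses the first dose. A baseline item filled that way describes a treated patient, and it outranks a screening lab that was taken before treatment and would have served.

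Baseline variables used to form subgroups or adjust models should not be open to influence from treatment. Several SLEDAI-2K lab items are ones the drug might change: Section 2.1 lists C3, C4 and anti-dsDNA among the pharmacodynamic endpoints. Section 7.1.1 repeats the Day 210 SRI-4 analysis in every Section 4.2 subgroup, and Section 4.1 allows sensitivity analyses with covariates based on those subgroups. A misfilled baseline would therefore reach some efficacy outputs as well as the descriptive tables.

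**Working it through.** The plan states no figure for this point to reproduce. The check is a reading of the rules in sequence, followed by a count of the points exposed.

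**Step 1: follow the cross-reference.** Sections 4.2 and 6.4 point to Section 7.1. For missing pre-treatment data, Section 7.1.1 gives only an exclusion and no filling rule. The lab-item rules that can be borrowed are therefore those in Table 1 and the general rule in Section 5.4.

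**Step 2: apply the borrowed rule at Day 0.** Take a patient with no Day 0 complement result, a screening result within the previous 30 days and an unscheduled lab on Day 10.

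| Rule | Value used for baseline complement |
|---|---|
| Section 5.4 LOCF rule / Table 1 order | Day 10 lab (within 14 days after), which is post-dose |
| Section 5.4 baseline definition | Screening lab, which is pre-dose |

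The two rules give different source values for the same patient, and the plan does not say which prevails.

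**Step 3: mark the limits.** A wholly missing score is carried only from a prior visit (Section 5.4). CLASI has no lab items, and its totals are likewise carried only from a prior visit. The forward step therefore matters only for SLEDAI-2K lab items missing at baseline in a patient who also has an unscheduled lab in the next 14 days.

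**Step 4: points exposed.** From the form in Appendix 13.3:

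- All items: 8×8 + 6×4 + 7×2 + 3×1 = 64 + 24 + 14 + 3 = 105 over 24 descriptors, matching the range in Section 7.2.10.
- Lab items: urinary casts, hematuria, proteinuria and pyuria at 4 each; low complement and DNA binding at 2 each; platelets and white cells at 1 each. This gives 4×4 + 2×2 + 2×1 = 22 over eight descriptors.

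**Step 5: can one item change the class at 10?** Let *s* be the score without the item and *w* its weight. The item decides the class when *s* < 10 and *s* + *w* ≥ 10.

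| *w* | *s* for which the item decides the class | Score with the item present |
|---|---|---|
| 4 | 6 to 9 | 10 to 13 |
| 2 | 8 to 9 | 10 to 11 |
| 1 | 9 | 10 |

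A single filled item is enough, in either direction. The documents give no rate of missing Day 0 labs or of early unscheduled labs, so the number of patients affected cannot be calculated.

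**The case against.** The strongest defence is that the plan already contains the right answer. Section 5.4 restricts baseline to values on or before first dose, and Section 5.6 lets unscheduled data contribute to baseline. Together these send a missing Day 0 lab back to the latest pre-dose result. Sections 4.2 and 6.4 ask for methods consistent with Section 7.1, not identical to them; Table 1 is worded for Day 210; and carrying an observation forward ordinarily means looking back in time. Table 1 also allows clinical input before lock and unblinding when lab items are carried in either direction.

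Much of this stands. A careful programmer could reach the pre-dose derivation, so the text supports an unresolved conflict and not a settled rule that post-dose labs define baseline. It does not remove the problem. The forward step in Section 5.4 is written for any nominal visit, the baseline definition is only a default, and the clinical input is optional.

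A reader might infer several stronger things that the documents do not support:

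- *That the primary SRI-4 result is affected.* Sections 4.2 and 6.4 govern subgroups and summaries. Section 7.1.1 excludes patients with missing pre-treatment data from the primary analysis.
- *That Section 4.2 splits SLEDAI-2K at 10.* The subgroup list is redacted. The section shows that baseline SLEDAI is used, but the cut is visible only in Section 6.4.
- *That the plan contradicts itself on who is included.* Section 5.3 defines pre-treatment as the whole period before first dose, so a patient with a screening score is not plainly missing. The Section 7.1.1 exclusion already reads close to excluding only patients with no pre-dose value, so no gain in patients can be claimed from the fix.
- *That every value filled this way is wrong, or biased by arm.* The items are present or absent, so a post-dose lab may give the same score. The SAP has no data on differences by arm or on why early unscheduled labs are drawn.

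**Conclusion.** The point holds as a conflict between stated rules. The literal order of the borrowed lab rule allows a post-dose result to fill a missing baseline SLEDAI-2K item ahead of a usable pre-dose one, while the baseline definition forbids it, and the plan does not rank the two.

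Per patient, the ceiling is 22 of 105 points, reached only if all eight lab items are missing and differ. The realistic case is one or two items, which can still change the class at 10. Overall impact is probably low, because a missing Day 0 lab item and an unscheduled lab within 14 days must coincide; that is a judgement, since no frequency is available. The exposure is confined to the baseline disease tables, any SLEDAI-based subgroup in Section 4.2 and the optional covariate analyses. The conclusion assumes that dosing takes place at the Day 0 visit, as the schedule in Section 3.1 indicates. It is worth correcting because it is cheap and because leaving the choice until after unblinding would invite a post hoc decision.

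**What to change.** State in Sections 4.2, 5.4 and 6.4 that imputation of any baseline value uses only results collected on or before the date and time of first dose, and that the 14-days-after step for lab items therefore does not apply at baseline. In Section 5.4 the natural place is beside the lab-component rule, so that it and the baseline definition cannot be read against each other.

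The cost is one sentence in each of three places and one condition in the baseline SLEDAI-2K derivation, using data already collected. A patient whose only lab result for an item is post-dose would stay missing at baseline; Section 4.2 already excludes from subgroup analyses anyone lacking the subgroup parameter. The change should be made before unblinding.

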### 4.3. Multiple Comparisons and Multiplicity

The Type 1 error rate will not be adjusted for multiplicity.

## 5. GENERAL DATA HANDLING CONVENTIONS

## 5.1. Reference Dates

- Screening date is defined as the electronic case report form (eCRF) provided date on which a patient was screened for trial entry.
- Informed consent date is the date the patient signed the informed consent form.
- Randomization date is defined as the date on which the patient is randomized to study treatment.
- Treatment start date is defined as the date of first dose of study drug.
- Treatment end date is defined as the date of last dose of study drug.

- Age will not be calculated and will come directly from the eCRF. The eCRF uses the informed consent date as its reference date for age calculation.
- Safety data, such as AEs and laboratory assessments will use the treatment start date as a reference date.
- Efficacy data will use the randomization date as a reference date.
- Study day will be based on treatment start date as a reference date.

## 5.2. Study Day and Duration Variables

Reference date calculations will be defined as follows, assuming non-missing dates:

- date of interest – reference date + 1 when the date of interest is on or after the reference date;
- otherwise, date of interest – reference date.

If either date is missing or incomplete, reference date calculations will not be performed. Date imputation will be performed as identified in Section 5.5.

Study day will either have a negative value if collected before dosing or a positive value if collected on or after the day of drug dosing; there will be no study day zero.

Duration of time is dependent on reference dates and will be calculated in a manner similar to that of the reference date calculation. Duration on study is defined as the end of study date – informed consent date + 1. Duration of treatment is defined as treatment end date – treatment start date + 1, where treatment end date is the date of last dose of study drug.

Time-to-event endpoints are followed until first event or censoring. As a result, event time will be calculated as: event or censoring date – reference date + 1. These are further described in Section 7.

When reporting time-to-event data (TTMF and time to BILAG A flare or >1 BILAG B flare) or duration outcomes, the results (in days) above will be converted to an appropriate unit. When reporting in months it will be divided by 30.4375; for reporting in weeks it will be divided by 7; and for reporting in years it will be divided by 365.25.

## 5.3. Study Time Periods

Where applicable, data reporting will be classified by the following study periods for analysis:

- Pre-treatment is defined as the period prior to a patient's treatment start date.
- On-treatment is defined as the period between a patient's treatment start date and treatment end date, inclusive.
- Post-treatment is defined as the period of time following the on-treatment period.

